7. DIET/ACTIVITY/OTHER CONSIDERATIONS

Diet

Subjects should maintain a normal diet unless modifications are required to manage an AE such as diarrhea, nausea or vomiting.

Contraception

Pembrolizumab may have adverse effects on a fetus in utero. Furthermore, it is not known if pembrolizumab has transient adverse effects on the composition of sperm. For this trial, male subjects will be considered to be of non-reproductive potential if they have azoospermia (whether due to having had a vasectomy or due to an underlying medical condition).

Female subjects will be considered of non-reproductive potential if they are either:

- (1) Postmenopausal (defined as at least 12 months with no menses without an alternative medical cause; in women <45 years of age a high follicle stimulating hormone (FSH) level in the postmenopausal range may be used to confirm a post-menopausal state in women not using hormonal contraception or hormonal replacement therapy. In the absence of 12 months of amenorrhea, a single FSH measurement is insufficient.);

OR

- (2) Have had a hysterectomy and/or bilateral oophorectomy, bilateral salpingectomy or bilateral tubal ligation/occlusion, at least 6 weeks prior to screening;

OR

- (3) Has a congenital or acquired condition that prevents childbearing.

Female and male subjects of reproductive potential must agree to avoid becoming pregnant or impregnating a partner, respectively, while receiving study drug and for 120 days after the last dose of study drug by complying with one of the following:

- (1) Practice abstinence[†] from heterosexual activity;

OR

- (2) Use (or have their partner use) acceptable contraception during heterosexual activity.

Acceptable methods of contraception are[‡]:

Single method (one of the following is acceptable):

- Intrauterine device (IUD)

- Vasectomy of a female subject's male partner
- Contraceptive rod implanted into the skin

Combination method (requires use of two of the following):

- Diaphragm with spermicide (cannot be used in conjunction with cervical cap/spermicide)
- Cervical cap with spermicide (nulliparous women only)
- Contraceptive sponge (nulliparous women only)
- Male condom or female condom (cannot be used together)
- Hormonal contraceptive: oral contraceptive pill (estrogen/progestin pill or progestin-only pill), contraceptive skin patch, vaginal contraceptive ring, or subcutaneous contraceptive injection

†Abstinence (relative to heterosexual activity) can be used as the sole method of contraception if it is consistently employed as the subject's preferred and usual lifestyle and if considered acceptable by local regulatory agencies and ERCs/IRBs. Periodic abstinence (e.g., calendar, ovulation, sympto-thermal, post-ovulation methods, etc.) and withdrawal are not acceptable methods of contraception.

‡If a contraceptive method listed above is restricted by local regulations/guidelines, then it does not qualify as an acceptable method of contraception for subjects participating at sites in this country/region.

Subjects should be informed that taking the study medication may involve unknown risks to the fetus (unborn baby) if pregnancy were to occur during the study. In order to participate in the study subjects of childbearing potential must adhere to the contraception requirement (described above) from the day of study medication initiation (or 14 days prior to the initiation of study medication for oral contraception) throughout the study period up to 120 days after the last dose of trial therapy. **If there is any question that a subject of childbearing potential will not reliably comply with the requirements for contraception, that subject should not be entered into the study.**

Use in Pregnancy

If a subject inadvertently becomes pregnant while on treatment with pembrolizumab, the subject will immediately be removed from the study treatment. The site will contact the subject at least monthly and document the subject's status until the pregnancy has been completed or terminated. The outcome of the pregnancy will be reported to the Sponsor and to Merck without delay and within 24 hours to the Sponsor and within 2 working days to Merck if the

outcome is a serious adverse experience (e.g., death, abortion, congenital anomaly, or other disabling or life-threatening complication to the mother or newborn).

The study investigator will make every effort to obtain permission to follow the outcome of the pregnancy and report the condition of the fetus or newborn to the Sponsor. If a male subject impregnates his female partner the study personnel at the site must be informed immediately and the pregnancy reported to the Sponsor and to Merck.

Use in Nursing Women

It is unknown whether pembrolizumab is excreted in human milk. Since many drugs are excreted in human milk, and because of the potential for serious adverse reactions in the nursing infant, subjects who are breast-feeding are not eligible for enrollment.

Subject Withdrawal/Discontinuation Criteria

Subjects may withdraw consent at any time for any reason or be dropped from the trial at the discretion of the investigator should any untoward effect occur. In addition, a subject may be withdrawn by the sponsor-investigator if enrollment into the trial is inappropriate, the trial plan is violated, or for administrative and/or other safety reasons.

A subject must be discontinued from the trial for any of the following reasons:

8. The subject or legal or legal representative (such as a parent or legal guardian) withdraws consent.
9. Confirmed extra- extra-cranial radiographic disease progression.
10. Unacceptable adverse experiences as described in section 6 and 7.
11. Intercurrent illness that prevents further administration of treatment.
12. Investigator's decision to withdraw the subject.
13. The subject has a confirmed positive serum pregnancy test.
14. Noncompliance with trial treatment or procedure requirements.
15. The subject is lost to follow-up.
16. Completed at least 24 months of uninterrupted treatment with pembrolizumab or 35 administrations of study medication, or whichever occurs last;

Note: 24 months of study medication is calculated from the date of first dose. Subjects who stop pembrolizumab after 24 months may be eligible for up to one year of additional study treatment at the discretion of their treating physician, especially if their disease is clinically stable;

17. Administrative reasons
18. Confirmed radiographic disease progression per RECIST criteria
 1. *Note: A subject may be granted an exception to continue on treatment with confirmed radiographic progression if clinically stable or clinically improved, please see Section 6 and 7.*

The End of Treatment and Follow-up visit procedures are listed in Section 10 (Protocol Flow Chart) and Section 11. After the end of treatment, each subject will be followed for 30 days for adverse event monitoring (serious adverse events will be collected for 90 days after the end of treatment). Subjects who discontinue for reasons other than progressive disease will have

post-treatment follow-up for disease status until disease progression, initiating a non-study cancer treatment, withdrawing consent or becoming lost to follow-up. After documented disease progression each subject will be followed by telephone for overall survival until death, withdrawal of consent, or the end of the study, whichever occurs first.

Discontinuation of Study Therapy after CR

Discontinuation of treatment may be considered for subjects who have attained a confirmed CR that have been treated for at least 24 months with pembrolizumab and had at least two treatments with pembrolizumab beyond the date when the initial CR was declared. Subjects who then experience radiographic disease progression may be eligible for up to one year of additional treatment with pembrolizumab via the Second Course Phase at the discretion of the investigator if no cancer treatment was administered since the last dose of pembrolizumab, the subject meets the safety parameters listed in the Inclusion/Exclusion criteria, and the trial is open. Subjects will resume therapy at the same dose and schedule at the time of initial discontinuation.

Clinical Criteria for Early Trial Termination

Early trial termination will be the result of the criteria specified below:

- 1) Quality or quantity of data recording is inaccurate or incomplete
- 2) Poor adherence to protocol and regulatory requirements
- 3) Incidence or severity of adverse drug reaction in this or other studies indicates a potential health hazard to subjects
- 4) Plans to modify or discontinue the development of the study drug

In the event of Merck decision to no longer supply study drug, ample notification will be provided so that appropriate adjustments to subject treatment can be made.

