3. OBJECTIVES, ENDPOINTS & HYPOTHESES

1. Primary Objective, Endpoint, & Hypothesis

Primary Objective

To evaluate the safety of concurrent single/low dose radiotherapy (**8 Gy/1fx**) in combination with Pembrolizumab in relapsed or refractory myeloma patients; **Once 10 patients are enrolled, we will stop trial for 3 months to assess for acute toxicity, and then resume the trial.**

Primary Endpoint

CTCAE > grade 2 toxicity at the specific irradiated **organ site at 3 months** (the Dose Limiting Toxicity);

Primary Hypothesis

The primary hypothesis of this pilot study is that the use of concomitant Pembrolizumab and radiation therapy in multiple myeloma patients will be well tolerated and safe.

Alternative Hypothesis

It is possible that concurrent use of radiotherapy and Pembrolizumab in relapsed/refractory myeloma may increase CTCAE > grade 2 toxicity within the radiated site at 3 months.

2. Secondary Objective(s), Endpoint(s) & Hypothesis (es)

Secondary Objectives

To characterize late toxicity (CTCAE > grade 2 toxicity at **6 and 12 months**) and the effect of radiation in combination with Pembrolizumab on systemic response rates using international myeloma working group (IMWG) uniform response criteria for multiple myeloma at **6 months and 12 months**;

To assess changes in PET/CT as a result of combining Pembrolizumab and radiotherapy at **6 months and 12 months**;

Secondary Endpoints

- a. 1. Number of patients achieving any response (from baseline) per IMWG response criteria at **6 months and 12 months**;
- b. 2. Overall survival time at **6 months and 12 months**;
- c. 3. Overall response based on baseline changes on PET/CT at **6 months and 12 months**;
- d. 4. Difference in pre and post treatment serum immune biomarkers;

Secondary Endpoint Definitions

- a. Response is defined per IMWG criteria, and will be calculated at **6 months and 12 months**;
- b. Overall survival will be defined as time from first treatment on cycle 1, day 1 to the earlier of date of death and/or last follow up at **6 months and 12 months**.
- c. Overall response will be defined using IMWG uniform response criteria.
- d. Several serum biomarkers will be analyzed.

Secondary Hypotheses

The secondary hypothesis is that low dose/single fraction (8Gy/1fx) will synergize with Pembrolizumab for a more effective anti-myeloma response per IMWG, via the radiation induced abscopal response.

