6. DOSE MODIFICATION, DOSE LIMITING TOXICITIES, AND SUPPORTIVE CARE

Dose modification and toxicity management for immune-related AEs associated with pembrolizumab

AEs associated with pembrolizumab exposure may represent an immunologic etiology. These immune-related AEs (irAEs) may occur shortly after the first dose or several months after the last dose of pembrolizumab treatment and may affect more than one body system simultaneously. Therefore, early recognition and initiation of treatment is critical to reduce complications. Based on existing clinical trial data, most irAEs were reversible and could be managed with interruptions of pembrolizumab, administration of corticosteroids and/or other supportive care. For suspected irAEs, ensure adequate evaluation to confirm etiology or exclude other causes. Additional procedures or tests such as bronchoscopy, endoscopy, skin biopsy may be included as part of the evaluation. Based on the severity of irAEs, withhold or permanently discontinue pembrolizumab and administer corticosteroids. Dose modification and toxicity management guidelines for irAEs associated with pembrolizumab are provided in **Table 2**.

Dose modification and toxicity management of infusion-reactions related to pembrolizumab

Pembrolizumab may cause severe or life threatening infusion-reactions including severe hypersensitivity or anaphylaxis. Signs and symptoms usually develop during or shortly after drug infusion and generally resolve completely within 24 hours of completion of infusion. Dose modification and toxicity management guidelines on pembrolizumab associated infusion reaction are provided in **Table 3**.

Other allowed dose interruption for pembrolizumab

Pembrolizumab maybe interrupted for situations other than treatment-related AEs such as medical / surgical events or logistical reasons not related to study therapy. Subjects should be placed back on study therapy within 3 weeks of the scheduled interruption, unless otherwise discussed with the Sponsor. The reason for interruption should be documented in the patient's study record.

TABLE 2: Dose Modifications and Toxicity Management of irAEs associated with Pembrolizumab**I General instructions:**

1. Corticosteroid taper should be initiated upon AE improving to Grade 1 or less and continue to taper over at least 4 weeks.

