selection ranging from 4 MeV – 20 MeV. For deeper seated tumors, photon therapy should be used with energy range of 4MV – 18 MV, based on appropriate coverage of the PTV. The goals should be to provide adequate coverage, while minimizing hot spots as well as scattered radiation dose to the surrounding structures.

A range of radiation fields are allowed. A single beam, an AP/PA, or multiple beams are allowed. A range of radiation techniques (2D, 3DCRT, IMRT, IMRS) are allowed;

Institutional standard of care protocol will be followed when assessing adequate PTV coverage and dose volume histogram normal tissue limits.

Radiation Toxicity Evaluation

Patients should undergo evaluation for development of acute and chronic radiotherapy toxicity at the time of protocol visits. This should be done at **1 month +/- 2 weeks** after completing radiotherapy and **every 3 months for at least 1 year**. Toxicity will be graded per CTCAE 4.0 adverse events grading system. If there is a suspicion of a novel or unexpected toxicity of grade 3 or higher severity that is suspected to be related to the combination of pembrolizumab and radiotherapy, the study coordinator should be immediately notified. If possible, a determination should be made whether the toxicity is likely to be the result of immune therapy, radiotherapy, or was exacerbated by the combination. The AE or SAE should be attributed as definite, probable, possible, or unlikely for each.

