11. STATISTICAL ANALYSIS PLAN

1. Statistical Analysis Plan Summary

Study Design

The study is a pilot study to look at the safety of concurrent PD-1 inhibitor and SRS for relapsed/refractory myeloma. A total of 24 patients will be enrolled on the trial (20 is the minimum, with an additional 4 patients, to make for any attrition and/or loss to follow-up). 12 patients will be allowed to not have measurable myeloma disease in this trial. Once 10 patients are enrolled, we will stop trial for 3 months to assess for acute toxicity, and then resume the trial. The estimated exact Clopper-Pearson 95% confidence interval for a 20% rate based on 5 responses in 20 patients is (0.087, 0.491), with a precision of 0.185. If we see lower than 20% difference in rate of toxicity at 3 months, the combination will be deemed safe.

A minimum of 20 patients are required to complete full treatments. An additional 20% is allowed for drop out/failure to adhere to required follow-up and treatment recommendations. Thus, 24 patients will be allowed to be enrolled on the trial to make for any attrition and/or loss to follow-up. 12 patients will be allowed to not have measurable myeloma disease.

# of Responses / # of Patients	95% confidence interval
5 / 20	(0.087, 0.491)
6 / 24	(0.098, 0.467)

Populations for analysis

- Enrolled set: All subjects who signed an informed consent.
- Safety set: All subjects who received at least one dose of any study drug.
- Full analysis set: All subjects from the safety set who have the required follow-up and treatment adherence to evaluate response and safety over time.

2. Statistical Analyses

1. Response

IMWG criteria will be used to assess response. Proportion of patients achieving stable

disease or better will be reported at **6 months** and **12 months**; Response rates will be reported along with 95% confidence intervals will be estimated using the Clopper-Pearson method.

2. Safety

Proportion of acute (at **3 months**) and late toxicity (**6 and 12 months**) will be reported, and 95% confidence intervals will be estimated using the Clopper-Pearson method.

3. Overall Survival

For overall survival, death from any cause will be defined as the event. Patients will be censored at time of last follow-up. OS will be estimated using the Kaplan-Meier product-limit method. Overall survival will be analyzed at **6 months, and 12 months**.

4. Biological variables

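### The 3-month irradiated-site toxicity rate can lose the patients who have the event: toxicity is a ground for leaving the trial, and no rule makes their events count

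*Combined protocol and SAP*

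**What the plan says.** **Exit.** Section 7 (Subject Withdrawal/Discontinuation Criteria) says a patient may "be dropped from the trial at the discretion of the investigator should any untoward effect occur". Its mandatory list opens with "A subject must be discontinued from the trial for any of the following reasons" and includes "Unacceptable adverse experiences as described in section 6 and 7". Section 6 acts on the drug alone: "Based on the severity of irAEs, withhold or permanently discontinue pembrolizumab and administer corticosteroids".

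**Endpoint.** Section 3 defines the primary endpoint as "CTCAE > grade 2 toxicity at the specific irradiated" organ site at 3 months. The footnote to the flow chart in section 9.1 has the irradiated site graded once each at 3, 6 and 12 months.

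**Follow-up.** After treatment ends, "each subject will be followed for 30 days for adverse event monitoring", and the same sentence extends collection to 90 days for serious events. Section 7 then follows patients who stopped without progression for disease status. Section 8 asks for radiation toxicity review at 1 month and "every 3 months for at least 1 year", at protocol visits. Section 10 follows adverse events present at withdrawal, and follows any event above grade 1 until it returns to grade 0-1 or new anti-neoplastic therapy begins.

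**Analysis.** Section 11 declares the combination safe if the 3-month toxicity figure is below 20%. It defines a Safety set of all patients given at least one dose of study drug, and a Full analysis set: "All subjects from the safety set who have the required follow-up and treatment adherence to evaluate response and safety over time". It assigns neither to the toxicity proportion. Four patients beyond the minimum of 20 are enrolled to cover attrition and non-adherence.

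**The concern.** The reason for exit overlaps with the outcome being measured. A patient with a severe reaction in the radiation field is among those most likely to stop early. That patient may have no month-3 grade and may fail the follow-up and adherence conditions of the Full analysis set. If the rate is computed on graded patients or on that set, events leave the numerator selectively and the rate is biased downward. This one proportion decides whether the combination is called safe, and with about 20 to 24 patients a single case can change the answer. Radiotherapy is complete on Day 1, so stopping pembrolizumab gives no reason to stop grading the site.

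**Working it through.** **1. The plan's own figures.** Clopper-Pearson limits are the 2.5% quantile of Beta(x, n-x+1) and the 97.5% quantile of Beta(x+1, n-x).
- 5/20: (0.087, 0.491)
- 6/24: (0.098, 0.467)

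Both match the table in section 11. Enrolment also reproduces: 20 × 1.2 = 24.

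**2. The decision rule at n = 24.** I read the rule as observed rate below 20%, which agrees with the goal in section 2. Then 4/24 = 16.7% (0.047, 0.374) passes and 5/24 = 20.8% (0.071, 0.422) does not.

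**3. Excluding k event patients from numerator and denominator: (x-k)/(24-k).**

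| Events among 24 | Excluded | Reported | Verdict |
|---|---|---|---|
| 5 (20.8%) | 1 | 4/23 = 17.4% | safe |
| 6 (25.0%) | 2 | 4/22 = 18.2% | safe |
| 7 (29.2%) | 3 | 4/21 = 19.0% | safe |

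With nobody excluded, none of the three would be called safe.

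**4. Chance of a safe verdict.** Let X ~ Bin(24, p) be the events and Y ~ Bin(X, q) the event patients excluded. The verdict is safe if (X-Y)/(24-Y) < 0.20. The values of q are assumptions, since the documents give no rate of exit for toxicity.

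| True rate p | q = 0 | q = 10% | q = 25% | q = 50% |
|---|---|---|---|---|
| 25% | 0.247 | 0.344 | 0.509 | 0.770 |
| 30% | 0.111 | 0.182 | 0.324 | 0.612 |

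The expected reported rate is p(1-q)/(1-pq). At p = 30% it is 24.3% for q = 25% and 17.6% for q = 50%. If the event patients instead stay in the denominator as non-events, the direction is the same: 0.344 at q = 25% and 0.713 at q = 50%.

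**5. Losses among patients without the event.** Let each non-event patient also be lost with probability r. At p = 30% and q = 25%, the chance of a safe verdict falls from 0.324 to 0.211 for r = 1/6, and to 0.167 for r = 25%. In the last case the losses are equal and the expected rate is unbiased at 30%. The remaining excess over 0.111 comes from the smaller sample.

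**6. Adverse event window.** The flow chart puts doses on Day 2-3, Day 22 and every 21 days after that, so doses 3 and 4 fall on Days 43 and 64. I take the last dose as the end of treatment and add 30 days.

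| Last dose | All adverse events to | Serious events (+90) to |
|---|---|---|
| 1 | Day 32-33 | Day 92-93 |
| 2 | Day 52 | Day 112 |
| 3 | Day 73 | Day 133 |
| 4 | Day 94 | Day 154 |

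Month 3 is about Day 91. After doses 1 to 3, routine collection closes before month 3 and serious-event collection does not. The section 10 reporting rule for serious events shortens to 30 days after treatment stops if new anticancer therapy starts.

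**The case against.** The strongest reply is that the trial in section 7 loosely means trial treatment. The same mandatory list includes completing 24 months of drug, its closing text describes follow-up after discontinuation, and section 6 stops only pembrolizumab. Section 10 requires a safety visit about 30 days after the last dose and follows every event above grade 1, which covers every primary event. Serious events are collected for 90 days. The radiation toxicity review in section 8 runs from radiotherapy and is not conditioned on drug. Section 11 also offers a Safety set with no follow-up requirement. Finally, losses among non-event patients push the rate up: 4/24 passes, but losing four such patients gives 4/20 = 20.0%, which does not.

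Most of this stands. A reader might infer that patients with toxicity necessarily vanish from observation, or that their events go unrecorded. The documents do not support that: an event present at exit would usually be recorded and followed.

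Two gaps remain. Recording an event does not make it count in a proportion that is graded once at month 3, has no named analysis set and has no rule for a missing grade. And a new, non-serious in-field event after the 30-day window may be missed in a patient who stopped after doses 1 to 3, because section 8 does not say that its visits continue after exit.

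**Conclusion.** The point holds as a defect in how the primary rate is counted, with a smaller gap in site grading after early stopping. Followed as written, the plan permits event patients to be excluded from the proportion that decides safety. It does not require this, because an analyst could choose the Safety set and the worst grade.

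At the decision boundary one excluded event patient is enough (5/24 against 4/23). At a true 30% rate the chance of a safe verdict goes from 11% to between 18% and 61% for exclusion of 10% to 50% of event patients only. It is about 21% if 25% of event patients and one sixth of non-event patients are lost. These figures rest on assumed, independent loss fractions and on reading the rule as an observed rate below 20%. They show sensitivity and do not forecast the bias; the documents give no basis for choosing among them.

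**What to change.** **Section 11.** Base the 3-month toxicity proportion on the Safety set. Count the worst irradiated-site CTCAE grade from Day 1 through month 3, so that any site event above grade 2 seen before a patient stops or leaves is an event. Do not remove or replace patients who stop for toxicity. State how a patient with no event and no month-3 grade is handled, and report how many there are. Because the Safety set is defined by study drug, also say whether an irradiated patient who never receives pembrolizumab belongs to it.

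**Sections 8 and 9.1.** State that irradiated-site grading at 3, 6 and 12 months continues whatever the pembrolizumab status, unless the patient dies, withdraws consent or is lost to follow-up.

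**Sections 6, 7 and 10.** The sponsor should reconcile discontinuation from the trial in section 7 with the drug-level wording in section 6 and with the follow-up described in sections 7 and 10. How the stopping rules themselves should read is for the sponsor.

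**Cost.** Protocol and SAP wording only. The radiation oncology visits are already scheduled, and the reported rate may be slightly less favourable.
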